5.7 Withdrawal of Subjects

We do not and cannot anticipate any circumstance under which subjects will be withdrawn from the research without their consent. There will be no consequences if a subject decides to withdraw from the study. Indeed, the voluntary nature of the study will be stressed during the informed consent process. Contact information for study personnel will be given to each participant.

6.0 Reporting

We do not anticipate any serious events. If the respondent exhibits adverse reactions, such as shame, during the interview portion of the study, every effort will be made to encourage him or her and they will be reminded of their rights as participants. A highly trained and experienced interviewer will conduct the interviews.

If participants voice suicidal ideation/plan this will be reported as a SAE or UAP.

We will inform the Central IRB of any unanticipated problems through information reporting and continuing reviews.

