Data Collection Methods: After informed consent and randomization, participants will complete baseline study measures. At follow-up, participants will be re-assessed using the same measures via mail, telephone or in person with telephone reminders, if needed. In addition, Concussion Coach will also collect the extent of their interaction with the application during their participation.

Individual interviews will be conducted with at least 10% of the Concussion Coach users to evaluate their perception and satisfaction with other TBI-related education received within the VA to date, their overall satisfaction with Concussion Coach e.g. its ease of use, perceived barriers and facilitators to the use of the App, behavioral intention to use Concussion Coach in the future and recommendations for improving it. This 10% sample will not be random – rather we will solicit interviews from those who improved using PCS Concussion Coach, those who did not get better or became worse, and those who did not use the App during the study period or used it infrequently. In addition to qualitative questions about barriers and facilitators, interview questions will include quantitative assessment of satisfaction (e.g., rating scales of satisfaction). Interviews will be conducted by experienced trained interviewers (e.g., [name]) and will be audio recorded. Participants will already be consented in person or over the telephone, so the interviewer will identify and briefly recap the consenting process, the project, and then ask permission for audio tape recording the interview. Interviews will be conducted by phone or in person based on participant convenience. The interviewer will use standard communication techniques to stimulate discussion such as generic prompts (tell me more), summarizing statements, silence, and eye contact. If the respondent exhibits adverse reactions, such as shame, during the interview, every effort will be made to encourage him or her and they will be reminded of their rights as participants.

Risk Minimization Plan:

The educational program is self-administered and participation is strictly voluntary. There are no known risks involved. The PI will inform participants of all methods used to maintain confidentiality of information. Participants will be assured of the confidentiality of the data and that no one outside of the research team will have access to the raw data.

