Safety Plan: If participants voice suicidal ideation/plan either in person or via telephone to study staff, hospital policy will be followed. There are specific policies in place for crisis management both via telephone and in person. All research personnel with participant contact will be trained according to this policy. In addition, interviewers and research assistants will be trained by the PI on how to identify and respond to participants in distress. This will occur through role play, readings, and other pre-study group trainings. All proposed pertinent study personnel have clinical training/experience and suicide/violence assessment experience. They will follow VA Suicide Prevention guidelines and are required to have had all VA research trainings which include Suicide Prevention guidelines.

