5.5 Study Evaluations

Table 1 outlines quantitative measures we propose to use. Examination of potential mediator and moderator variables will allow us to determine who is most likely to benefit from the intervention (e.g., people with limited social support, people who are less 'tech savvy') and qualify our findings. Justification for each of these included variables is contained in the description of each measure below the table.

Table 1. Study Measures

Construct	Tool	Timepoint
Primary Outcomes		
PCS	Neurobehavioral Symptom Inventory (NSI)	Baseline, up to 1 year later
Symptom Exaggeration	mBias	Baseline, up to 1 year later
Psychological Distress	Brief Symptom Inventory (BSI) PCL-5 Strong Star (PCL)	Baseline, up to 1 year later

Time Spent on Concussion Coach in total and on various components	Concussion Coach download	Duration of study i.e. a 3 month period for use of APP
PCS	NSI from Concussion Coach download (could be multiple NSIs depending on subject)	Duration of study i.e. a 3 month period for use of APP
Barriers and Facilitators of Concussion Coach use and effectiveness	Concussion Coach Interview Follow-Up Data Form	Up to 1 year later for Follow-Up Form. Interview date is an undetermined time after the final study visit.
Potential Mediators		
Perceptions and Knowledge of Illness	TBI Education Satisfaction, Knowledge, and Attributions	Baseline, up to 1 year later
Self-Efficacy	Self Efficacy for Symptom Management Scale (SEsx)	Baseline, up to 1 year later
Potential Moderators		
Social Support	Social Support Questionnaire – Short Form (SSQSR)	Baseline, up to 1 year later
Comfort with Technology	eHealth Literacy Scale (eHEALS)	Baseline, up to 1 year later
Use of Apps during study period	Follow-Up Data Form	Up to 1 year after Baseline
Mental Health Treatment during study period	Follow-Up Data Form	Up to 1 year after Baseline
Demographics, Health and Disability Status		
Age, gender, diagnosis, comorbidities, other injuries.	Medical Record: Participant Information Form Enrollment Participant Information Form	Baseline

Primary Outcome Measures:

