Individual interviews (see Appendix for script) will be conducted with 10% of the Concussion Coach users at study end to evaluate their satisfaction with Concussion Coach, ease of use, their perception and satisfaction with other TBI-related education they have received within the VA to date, barriers and facilitators to use of Concussion Coach, and behavioral intention to use Concussion Coach in the future. This 10% sample will not be random – rather, we will solicit interviews from those who improved on PCS using Concussion Coach, those who did not get better or became worse, and those who did not use the App during the study period or used it infrequently. In addition to qualitative questions about barriers and facilitators, interview questions will include quantitative assessment of satisfaction (e.g., rating scales of satisfaction). Interviews will be conducted by experienced trained interviewers (i.e., [name]) and will be audio recorded. Participants will already be consented in person or over the telephone, so the interviewer will identify and briefly recap the project, and then again ask permission for audio tape recording. Interviews will be conducted by phone or in person based on participant convenience. The interviewer will use standard communication techniques to stimulate discussion such as generic prompts (e.g., tell me more), summarizing statements, silence, and eye contact, if conducted in person. If the respondent exhibits adverse reactions, such as shame, during the interview, every effort will be made to encourage him or her and they will be reminded of their rights as participants.

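### No adverse-event question is put to both arms and no harms summary by arm is planned, so discrete events rest on passive reporting (minor)

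*Combined protocol and SAP*

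**What the plan says.** **Interview text.** Section 6.0 describes how staff respond "If the respondent exhibits adverse reactions, such as shame, during the interview portion of the study". Similar guidance appears in sections 5.1 and 5.5. It covers encouragement and a reminder of rights, not recording or analysis. Section 5.1 states "Individual interviews will be conducted with at least 10% of the Concussion Coach users" and adds "This 10% sample will not be random": people are sought according to symptom change or low app use. Table 1 adds "Interview date is an undetermined time after the final study visit". No interview of controls is described.

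**Routes open to both arms.** Section 6.0 also says "If participants voice suicidal ideation/plan this will be reported as a SAE or UAP" and promises that unanticipated problems go to the Central IRB. The Safety Plan in section 5.1 says "If participants voice suicidal ideation/plan either in person or via telephone to study staff, hospital policy will be followed", and it trains research assistants as well as interviewers to recognise distress. Section 8.0 has serious adverse events and unanticipated problems passed to the second site. None of this is restricted to one arm.

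**Follow-up data.** Section 5.1 allows reassessment by mail, telephone or in person. Table 1 schedules the NSI, BSI-18 and PCL-5 at baseline and follow-up, and a Follow-Up Data Form whose listed topics include "Mental Health Treatment during study period". Adverse events are not a listed topic of any measure.

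**Analysis.** Section 5.6 covers Hypotheses 1 to 4. Hypothesis 1 compares symptom severity and psychological distress by randomised group, adjusted for baseline. No tabulation of harms is described.

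**The concern.** The protocol itself gives a reason to look for harm. Section 2.0 reports that drawing attention to the TBI label can increase symptom reporting, and the app delivers TBI content, repeated symptom self-assessment and reminders. Section 5.1 nevertheless asserts that there are no known risks and that benefit far outweighs risk.

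Hospital admission, emergency care, self-harm or a new head injury would come to light through the described routes only if a participant raised it or staff happened to learn of it. If the chance of that differs by arm, a difference in counts may reflect contact rather than harm, and a count of zero may mean that nobody asked. Events that were never asked about are hard to recover at the analysis stage.

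**Working it through.** **1. The routes side by side**

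| Route | Who is covered | How a problem surfaces | By-arm analysis planned |
|---|---|---|---|
| Interview guidance (5.1, 5.5, 6.0) | about 10% of app users, purposive | upset seen during the interview | none |
| Suicidal ideation (5.1, 6.0) | all participants | must be voiced; the Safety Plan specifies in person or by telephone | none |
| Unanticipated problems (6.0, 8.0) | all participants | no question elicits them | none |
| NSI, BSI-18 (5.5, 5.6) | both arms at T2 | asked of everyone | yes, continuous scores under Hypothesis 1 |
| PCL-5 (5.5) | both arms at T2 | asked of everyone | unclear: section 5.5 names the BSI-18 global index for the primary distress analysis |

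The first three rows could register a discrete event, but all are passive. The last two ask everyone, but they measure severity on a scale. A difference in means can conceal a minority who deteriorate, and it does not show discrete events.

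**2. How contact can differ by arm**

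A participant followed up by mail may have no live conversation with staff after baseline. Interviewees, all app users, have one more. The Abstract reports 24 interviews among 419 enrolled. Assuming 1:1 allocation (the ratio is not stated), app users number 419 / 2 = 209.5. The extra contact reaches 24 / 209.5 = 11.5% of app users and 0% of controls. This sizes the difference in contact. It is not a basis for a harm rate, because nothing describes the interview as asking about events during app use.

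**3. The plan's expected sample**

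Section 5.6: (20 × 33 + 150) × 0.60 × (1 − 0.20) = 388.8, stated as 388. It reproduces. At 1:1 this is 194 per arm.

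**4. What a T2 question could still deliver**

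If n people are asked and none reports an event, the one-sided 95% upper bound on the event rate is 1 − 0.05^(1/n).

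- Goal: 419 / 0.93 = 450.5, so about 31 remain to be enrolled. If they alone were asked, 31 × 0.80 / 2 = 12.4, about 12 per arm. Bound: 1 − 0.05^(1/12) = 22.1%.
- If everyone enrolled so far could be asked: 419 × 0.80 / 2 = 167.6, about 168 per arm. Bound: 1.8%.
- At the plan's 194 per arm: 1.5%.

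The number already past T2 is not given. The first two cases bracket the current cohort, and the upper one is out of reach to the extent that T2 is already complete.

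**5. Power for a formal comparison**

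With 194 per arm, two-sided alpha 0.05 and assumed event rates, the normal approximation for two proportions gives 46% power for 5% against 10%, and 91% for 5% against 15%. Fewer people asked would lower both. The result should be reported as counts with intervals, not as a test.

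**The case against.** The strongest case against is that safety reporting already exists and suits a self-administered education app. Voiced ideation and unanticipated problems are reported without restriction to one arm, research assistants are trained to identify distress, and section 8.0 provides for communicating serious events. The harm that section 2.0 makes most plausible, more symptom reporting, would appear in the Hypothesis 1 comparison. All of this stands.

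It also defeats two stronger readings that a reader might infer. One is that the interview is the trial's sole harms check, so that harms could be recorded in the app arm alone. Section 6.0 itself contradicts this, and the interview sentence concerns upset caused by the interview. The other is that no harm can be compared between arms. That is wrong for average symptoms and distress, which are measured in both arms. It would likewise be a mistake to derive an upper limit on harm during app use from the 24 interviews.

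Three further objections carry weight. The items of the Follow-Up Data Form are not shown, so its content is inferred from topic labels. It does collect mental health treatment, a partial proxy for deterioration. The interview adds contact for about one app user in nine, after the final visit, so the imbalance from that source is modest. And a new question arrives late, with enrolment at 93% of goal.

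These limit the size of the point without removing it. The routes that could register a discrete event still depend on someone raising it, and no summary by arm is specified.

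**Conclusion.** The point holds as a minor one. Beyond spontaneous reporting of suicidal ideation and unanticipated problems, which covers both arms, the visible plan asks no adverse-event question systematically in both arms and specifies no harms summary by arm. Counts of discrete events by arm would be open to detection bias. Average worsening of symptoms and distress can be compared through the NSI and BSI-18 under Hypothesis 1.

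No harm rate can be put on the gap from these documents. The gain from a T2 question depends on how many people can still be asked: the zero-event upper bound per arm runs from about 22% (12 asked) to 1.8% (168 asked). This assumes 1:1 allocation, the plan's 20% attrition, and that the Follow-Up Data Form does not already contain such items.

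**What to change.** - **Form.** Check the Follow-Up Data Form. If it has no such items, add a short block, worded identically for every participant in both arms. It should cover hospital admission or emergency visit, self-harm, new head injury, and any problem the participant links to taking part, since baseline. The study team must reconcile the handling of answers on mailed forms with the existing Safety Plan, which is worded for in-person and telephone contact.
- **Events table.** Report counts by randomised arm with confidence intervals among those asked, stating the number asked in each arm.
- **Worsening.** Using data already collected, pre-specify a by-arm summary of the proportion worsening from baseline to T2 on the NSI, BSI-18 and PCL-5. Define worsening before outcomes are examined by arm. This covers everyone followed up, including those who miss the new block.
- **Interviews.** Report reactions seen in interviews separately, outside the comparison between arms.

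The cost is a form amendment, one or two minutes per participant and a small addition to the analysis plan. Participants already past T2 would lack the block, so the events table would describe part of the sample and should say so.

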7.0 Privacy and Confidentiality

We are requesting a HIPAA waiver for identification of potential participants. Without identifying potential participants (with a medical history of concussion), we would need to screen all patients within our two sites somehow, and make them go through a redundant evaluation to determine that they've had a concussion. This would be incredibly inefficient, since we are only targeting people who have had a concussion. The VA has a screening and evaluation process in place that can help us hone in on participants who might benefit and are eligible for this study. Identifying subjects that meet inclusionary criteria and garnering contact information requires access to the protected health information. Without this information, there is no practical means of contact within the context of this study. Gaining consent from the entire VA patient population is impractical.

In addition to diagnosis, we will need name and mailing address since we would like to send letters, asking potentially eligible participants (those with history of concussion) if they would be interested in participating. We will get this information from CPRS data from both Tampa and Bay Pines VA. We will also request national data on the TBI evaluation results from the appropriate sources (VHA Support Service Center (VSSC), national PM&R office national data system).

After participants are identified, no longer will any PHI be tied to an individual participant. In other words, data will be linked to a specific subject by a code rather than a direct identifier. There will be no identifying information on the questionnaire data, the interview data, or in the electronic data that is transmitted from the smart phone application to the server.

Patient data will be kept on networked, password protected VA computers and on VA servers in files with access limited to study personnel. Hard copies of the Informed Consent Forms and other data collection instruments are kept in locked file cabinets in an office that is kept locked when unoccupied. HIPAA privacy rules will be strictly maintained. Data will not be shared with anyone other than who is named in the consent form. All paper records will be maintained in locked files within a locked office. All electronic study data will be stored on a password protected database with access limited to select research personnel and will be encrypted and protected by firewall per VA guidelines. The PI and all study personnel will be responsible for ensuring that the research is conducted in a manner consistent with the ethical principles outlined in the Belmont Report, and in compliance with USF policies and procedures. A similar smart phone application has already been developed by the VA. It will be encrypted and the encryption will be FIPS 140-2 validated.

8.0 Communication Plan

All local site approvals will be obtained and maintained by the Lead Site (Tampa)'s study coordinator. If there are any problems, this will be communicated to the PI who will work to resolve it with the site PI at Bay Pines.

The lead study coordinator at Tampa will be responsible for keeping the Bay Pines study staff informed of any changes to study procedures, any changes required in documentation, any serious adverse events or unanticipated problems. The PI will inform Bay Pines study staff of any interim results that may impact the conduct of the study.

Regular, scheduled communication will occur between Tampa and Bay Pines via email and telephone. In person meetings will occur as necessary. As the PI has worked with the site PI and co-investigator at Bay Pines in the past, we do not anticipate any problems with communication.

The study will be largely implemented at Bay Pines by the site coordinator at Bay Pines ([name]), with oversight from the site PI.

All personnel involved in the study will be trained by the PI to ensure that the study is faithfully carried out and implemented. Regular communication will also facilitate this. When the study is over, the PI and primary study coordinator will ensure that the Bay Pines site is aware.

